- Presence of other known medical or psychiatric comorbidity that in the investigator's opinion would compromise participation in the study
- For Aim 2, MEG/MRI contraindications
- Any other Axis 1 disorder (unless secondary to depression for depressed group in Aim 2)
- History of psychosis
- Not fluent in English

5) Multi-Site Research

N/A

6) Study Timelines

For Aim 1, individual participant's involvement will last 2-3 hours during 1 day. For Aim 2, individual participant's involvement will last 4-7 hours over 1-2 days. Both aims have a longitudinal component where we will perform a phone interview 3-6 months after the initial assessment. This phone interview consists of a Beck Depression Inventory and is described more in detail in Section 9. We anticipate ongoing enrollment of participants for five years.

7) Study Endpoints

N/A

8) Study Methods

Participants will be asked to complete the following procedures:

Magnetic Resonance Imaging (MRI) scan(s) that may or may not involve simultaneous functional or cognitive tasks. Participants will lie down on a table and be placed into a long donut-shaped magnet. During the scan, participants may be shown pictures and/or words and will be asked to make decisions about the information presented in them. This takes about 1 hour.

Electroencephalograph (EEG) may be done at the same time as the MRI or MEG scan. If so, the participant will wear a cap during the MRI/MEG to record brain waves. Alternatively, the EEG may be performed separately. This takes about 2 hours.

Magnetoencephalography (MEG) records the magnetic activity of the brain at rest and while a person works on a set of tasks. It is performed while sitting in a comfortable chair in a special, magnetically shielded room. MEG does not emit radiation or magnetic fields. Electrodes will be applied to the participant's head and face using a special conductive gel. These will be held in place with a cap or sticky tape. These electrodes are used to monitor brain activity, eye movements, head position, and heartbeat. When the scan is over, all of the electrodes will be removed. This takes about 1 hour of assessment and up to 1 hour of setup.

Neurocognitive testing: In order to examine specific cognitive mechanisms that may be associated with neuropsychiatric disorders, participants will be asked to complete tasks (e.g. remembering letters or numbers, deciding between different monetary options) for up to 2 hours of total testing.

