A safety monitoring play will be followed to protect against intent for self-harm. All questionnaire scales will be immediately (within 1 day) examined for endorsement of suicidal ideation. If the participant endorses suicidal ideation (scoring 2 or 3 on item #9 of the Beck Depression Inventory) the PI will be immediately notified. The participant will then be contacted in person or over the phone by a senior member of the research team. Initially, the PI will lead all phone contacts and will use these as training experiences for other senior members of the research team (PhD student or post-doc level). The PI has extensive experience with these phone screening procedures: he was in a mood and anxiety disorders laboratory during PhD training at the University of Arizona and was trained by the clinical psychologist PI on these procedures for his multi-year dissertation work on major depression. This phone screen protocol consists of multiple steps to protect participant confidentiality:

- 1) The experimenter will verify via person-to-person contact with the participant that this is a “*good time to talk discretely*” prior to raising the reason for the call about the depression rating score for suicidality.
- 2) If the participant endorses thoughts of suicidality they will be notified of number of local counseling and psychiatric resources, including 24 hour hotlines and free or low cost counseling services. A list of these resources has been attached to this submission.
- 3) If the participant endorses imminent suicidal ideation, the PI will call 911 to inform emergency responders of the participant’s location and imminent suicide plans. Note that this is likely to be very rare.

There are risks of loss of privacy, getting insured, being employed, and stigmatization.

General (uncommon) risks: Participation in this study may result in discomfort, emotional stress, behavioral fatigue, and inconvenience.

Privacy and Confidentiality: Participation in this study may produce emotional stress, inconvenience or an invasion of privacy (uncommon). There is also a risk of breach of data confidentiality (uncommon).

There may also be side effects or risks to study participation that are unforeseen and not known at this time.

16) Potential Benefits to Subjects

Participants will receive a radiologist's review and report of their MRI scan and will be compensated for their time and inconvenience. No other direct benefit to participants is anticipated.

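### The 1-day outer limit for reading BDI item 9 lets an Aim 1a participant have the sadness induction and leave before a score of 2 or 3 is seen

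*Protocol*

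**What the plan says.** The rule is in protocol section 15 (Risks to Subjects): "All questionnaire scales will be immediately (within 1 day) examined for endorsement of suicidal ideation". The trigger and the response follow: "If the participant endorses suicidal ideation (scoring 2 or 3 on item #9 of the Beck Depression Inventory) the PI will be immediately notified". A senior team member then makes contact, either face to face or by telephone.

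On visit length, section 6 (Study Timelines) states: "For Aim 1, individual participant's involvement will last 2-3 hours during 1 day". For the other aim: "For Aim 2, individual participant's involvement will last 4-7 hours over 1-2 days".

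Section 8 (Study Methods) lists the BDI among the questionnaires and lets participants decline any question. It places the mood manipulation in the EEG session, directly before the tasks. In Aim 1a, non-depressed controls recall a sad event from their own lives while sad music plays. Sadness is rated before, after and at later points, and mood repair follows the tasks. Section 8 does not say when in the visit the BDI is completed.

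The SAP compares a sad with a neutral mood group by an independent-samples t-test.

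**The concern.** The stated deadline for reading item 9 outlasts the visit in which the induction is given. A participant who has already marked 2 or 3 could be asked to relive a sad personal event, finish the tasks and go home before anyone has looked at the form. The protocol treats that score as serious enough for immediate notice to the principal investigator, yet nothing makes the score known before the procedure meant to lower mood.

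The section 15 steps are also easier on site. A call made later depends on reaching the participant, finding a private moment and, in the worst case, telling emergency responders where the participant is.

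The departure half of the gap is not confined to Aim 1a. The same limit applies to depressed participants, 50 in each aim (section 25), although they do not receive the Aim 1a induction.

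**Working it through.** **Inputs from the documents**

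- Outer limit for reading the scales: 1 day (section 15).
- Visit length: 2-3 hours on one day in Aim 1; 4-7 hours over 1-2 days in Aim 2 (section 6).
- Enrollment: 150 controls and 50 depressed participants in Aim 1; 50 and 50 in Aim 2; 300 in total (section 25).

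**Assumptions**

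- One day is 24 hours and the BDI is completed at the start of the visit.
- Reading one item takes 1-3 minutes.
- Aim 1a has 100 to 150 controls, of whom 1 to 5 are not induced.

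**Step 1: the longest delay the rule permits.** Ceiling after departure = 24 hours minus visit length.

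- Aim 1: 24 − 3 = 21 hours to 24 − 2 = 22 hours.
- Aim 2, done in one day: 24 − 7 = 17 hours to 24 − 4 = 20 hours.

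If the BDI comes at the end of the visit, the ceiling is 24 hours. If one day means the same calendar day, reading after departure is still allowed for any visit that ends before the day does.

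**Step 2: does the order of the BDI matter?** If it precedes the induction, a completed answer can lie unread through both the induction and departure. If it follows the tasks, there is no answer to read at the time of induction, and departure can still come first. Either way the participant can be induced and leave before the score is seen.

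**Step 3: does another section close the gap?** Each relevant safeguard, set against the question of whether it is a stated check for suicidal ideation:

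- Non-depressed controls only (section 8): narrows the group. The structured clinical interview criterion in section 4 is stated for Aim 2.
- Exclusions (section 4): "Presence of other known medical or psychiatric comorbidity that in the investigator's opinion would compromise participation in the study", and other Axis 1 disorders. Suicidal ideation is not listed.
- Screening by phone or in person before the visit is scheduled (section 30): no question on ideation or item 9 is named.
- Sadness ratings and mood repair (section 8): directed at passing sadness.
- Power to end participation in the participant's best interest (section 14): cannot be used on an answer nobody has read.

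None is such a check.

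**Step 4: cost of reading item 9 on site.**

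- Staff time: 300 × 1/60 = 5 hours to 300 × 3/60 = 15 hours over the enrollment period.
- Precision: if *k* of *n* Aim 1a controls are lost in proportion from both groups, the standard error of the sad-neutral difference is multiplied by √(*n*/(*n* − *k*)).

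| *n* | *k* | Rise in standard error |
|---|---|---|
| 150 | 1 | 0.3% |
| 150 | 5 | 1.7% |
| 100 | 1 | 0.5% |
| 100 | 5 | 2.6% |
| 50 | 5 | 5.4% |

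The last row goes below the assumed range, because the Aim 1a sample size is not given.

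**The case against.** The strongest reply is that the rule's leading word asks for immediate review and that in-person contact is provided for. On that view, reading on site is foreseen, and the gap is only what a minimally compliant team could do. That is fair, and staff may already read the form during the visit. But the parenthesis says how late the review may be, and the steps in section 15 are written largely for telephone contact. Reading on site is allowed, not required.

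Second, the risk from the induction is largely handled: only non-depressed controls receive it, sadness is tracked, mood is repaired, and investigators can stop if they see distress. This stands as a reason to expect few cases. It does not replace reading the answer.

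Third, the size is unknown. There is no rate of item 9 scores of 2 or 3, no Aim 1a sample size and no sad/neutral split, so the number affected could be near zero. The hours measure permitted delay, not harm. All of this stands, and it limits the weight of the point.

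Fourth, the remedy reaches Aim 2, where no mood manipulation is used. The part tied to the mood procedure applies to Aim 1a alone. Reading before departure serves depressed participants in both aims and needs no separate form.

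Finally, the SAP, dated 03/15/2023, describes the sad-neutral comparison in the past tense. If Aim 1a is complete, the pre-induction step can no longer change its conduct, and the change matters only for any visits that remain.

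**Conclusion.** The point holds. As written, the rule permits item 9 to be read after both the induction and departure, and no other section prevents it. This follows from comparing a one-day limit with a 2-3 hour visit; it does not depend on where the BDI falls in the visit or on whether a day is 24 hours or a calendar day. The 21-22 hour ceiling for Aim 1 and the 17-20 hour ceiling for a one-day Aim 2 visit do depend on the 24-hour reading and on a BDI at the start.

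The induction can reach at most the 150 Aim 1 controls, and in fact fewer, because Aim 1b also uses controls and the SAP has a neutral group. The expected number scoring 2 or 3 cannot be estimated from the documents and is probably small. The change should be made because the consequence could be serious and the remedy is cheap. It is a participant-safety point and alters no statistical result in the plan. Confidence is medium.

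**What to change.** Amend sections 8 and 15 as follows:

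- Give the BDI at the start of the visit.
- In Aim 1a, read item 9 before the mood procedure, in the sad and neutral groups alike so that the comparison stays balanced.
- In both aims, read item 9 before the participant leaves.
- A participant scoring 2 or 3 goes to the existing contact steps in person and receives neither the sad nor the neutral procedure.
- A blank item 9 is asked about in person, before the mood procedure in Aim 1a and otherwise before departure. The participant may still decline to answer; a senior team member then decides whether to go ahead.
- Keep the one-day limit for the follow-up BDI completed online, and leave the item 9 threshold unchanged.

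The form is already in the battery. Beyond the 5-15 hours of reading, the main burden is having a senior team member reachable during visits at two locations (section 21) while enrollment runs: "We anticipate ongoing enrollment of participants for five years". That availability is not costed here. A few Aim 1a participants may be lost, with the small loss of precision shown above. A conversation about suicidality before the first sadness rating could affect that rating, but it would arise only with those who score 2 or 3, who are not induced, or who leave the item blank.

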Statistical Analysis Plan

NCT03856177

03/15/2023

In relation to ERP data, we first aimed to conceptually replicate and extend findings by Foti & Hajcak (2010) by assessing whether the RewP was affected by mood. An independent-samples t-test was conducted between mood manipulation groups (sad vs. neutral) to test whether sad mood could relatively reduce the RewP. The RewP was quantified as a reward-specific ERP component at electrode site FCz and amplitude was measured as the average amplitude within a 200–350ms time window. The electrode site and time window were decided a priori based on previous work utilizing the probabilistic selection task to investigate the RewP ([name] et al., 2019). Data were analyzed using the Jamovi toolkit in R. There was no adjustment for multiple comparisons correction.

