Protocol Title

Cognitive Neuroscience of Reward v12.19.18

1) Principal Investigator

[name], Department of Psychology, University of New Mexico
[name] [contact]

IRB Review History

N/A

2) Objectives

The electroencephalographic response known as the Reward Positivity (RewP) is a promising candidate biomarker of diminished valuation in anhedonia. The RewP is only elicited by the presentation of a rewarding outcome and it scales with the central feature of reinforcement learning models, the *positive reward prediction error* (+RPE). Thus, the RewP is specific and sensitive to +RPE, fulfilling the stringent criteria of being an invariant neural marker of this computational process. Importantly, the RewP is boosted by appetitive states and is diminished in depressed individuals, indicating that emotional processes influence this marker of reward learning. While prior work has effectively described these correlations (e.g. Foti and Hajcak, 2009), we do not know how emotion (e.g. depression) and +RPE interact to influence valuation. The objective of this proposal is to test whether mood directly diminishes +RPE coding in the RewP, or if these are separable influences on this signal.

Aim 1: To determine if affect and +RPE have independent or interactive effects on the RewP. Based on our working hypothesis, a sadness manipulation in healthy controls should diminish the RewP. Computational modeling will identify the parameters best associated with the influence of affect on learning, allowing us to capture the richness of these effects in an objective and consistent manner. Statistical modeling will quantify the independent vs. interactive influences of affective and +RPE processes on both the RewP and reward learning.

Aim 2: To determine if anhedonia and +RPE have independent or interactive influences on the source-level generators underlying the RewP. We will use gold-standard source-estimation techniques including concurrent EEG and MEG with MRI-based structural templates and an fMRI-based reward-localizer mask. These tools will be integrated to test our working hypothesis that anhedonia-specific reductions in the M/EEG RewP in depression will co-localize with +RPE in subgenual and ventromedial frontal cortex. This finding will identify a common mechanism for anhedonia-based reductions in reward responsivity.

3) Background

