The RewP is enhanced with positive affective manipulations (Brown & [name], 2018; Threadgill & Gable, 2017) and it scales with self-reported and behavioral reward responsiveness (Bress, Smith, Foti, Klein, & Hajcak, 2012). The RewP is diminished in depressed individuals (Bress et al., 2012; Foti & Hajcak, 2009), particularly a melancholic subtype closely related to anhedonia (Foti, Carlson, Sauder, & Proudfit, 2014; Liu et al., 2014). A reduced RewP is observed in children most vulnerable to depression (Kujawa, Proudfit, & Klein, 2014), and it can predict the probability of a future major depressive episode in never-depressed individuals (Bress, Foti, Kotov, Klein, & Hajcak, 2013). The RewP has good test-retest reliability (Kujawa et al., 2017; Levinson, Speed, Infantolino, & Hajcak, 2017) and internal reliability (Bress, Meyer, & Proudfit, 2015), including reliable diminution due to depressive symptoms (Bress et al., 2015). In sum, these findings demonstrate that the RewP has the sensitivity, specificity, validity, reliability, and prognostic value desired in a biomarker.

However, there is no formal model of the joint sensitivity of the RewP to emotion and +RPE signaling, and thus there is no explanation for the diminishment of this signal in depression. The core problem is that we do not know if emotion influences +RPE coding via the RewP. The statistical interaction of depressed mood and poorer +RPE encoding would identify the RewP as a mechanism of diminished valuation in anhedonia. Conversely, if these are independent influences on the RewP (i.e. main effects), then diminished valuation is likely to be encoded in the downstream targets of the generative area (likely striatum).

The current proposal addresses this hypothesis in separate aims that will manipulate this expression in healthy controls and assess these natural features in anhedonic depressed individuals. This contribution is expected to be significant because it will advance a translational mechanism for deficient valuation in anhedonia.

4) Inclusion and Exclusion Criteria

Inclusion criteria:

- Men or women aged 18-55
- In Aim 2, participants will need to either meet criteria for Major Depressive Disorder via a Structured Clinical Interview for the DSM-5 (SCID), or have an absence of symptoms to qualify as a control.
- Free from psychoactive medication for at least 2 weeks

Exclusion criteria:

- Participants unwilling or unable to give informed consent

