Participants will be asked to complete one or more of the following questionnaires:

- Demographics (age, gender, race, contact and alternate contact information, etc.)
- Handedness questionnaire
- Beck Depression Inventory (BDI)
- Mood and Anxiety Symptoms Questionnaire (MASQ)
- Behavioral Inhibition / Activation Scales (BIS/BAS)
- Snaith-Hamilton Pleasure Scale (SHAPS)
- Dimensional Anhedonia Rating Scale (DARS)
- Apathy-Motivation Index (AMI)
- Diagnosis information (SCID)

They may refuse to answer any question at any time. These questionnaires may take 2 hours to complete. Direct identifiers will be collected and maintained in the MRN COINS database. All data collected as part of this study will be coded with a Unique Research Subject Identifier (URSI).

Tasks: All tasks are NIMH Research Domain Criteria (RDoC) paradigms that have been previously utilized in studies of depression.

- 1) The Probabilistic Stimulus Selection task (Frank, Seeberger, & O'Reilly R, 2004) will be identical to the PI's previous work ([name] et al., 2010a, 2010b, 2011a, 2011b, 2014). The sophistication of the three separately valued training pairs facilitates a wide range of +RPE values and assessments of reward vs. punishment learning. During training, participants slowly learn to select the optimal item in each pair based solely on probabilistic reinforcement rates. EEG locked to the reinforcing feedback ("correct") elicits the RewP.
- 2) The Probabilistic Rewards task (Pizzagalli, Jahn, & O'Shea, 2005) will be used to assess a commonly-observed decrement in reward learning in depression (Bogdan & Pizzagalli, 2006; Pizzagalli et al., 2005; Vrieze et al., 2013).
- 3) The Gambling task (Foti & Hajcak, 2009) is an extremely rapid assessment (~5 minutes) of neural responses to reward and punishment.
- 4) The Effort Expenditure for Rewards Task (EEfRT: Treadway et al., 2009, 2013) measures a participant's willingness to press buttons over time in order to get reward.

Aim 1 will assess tasks 1,2, and 3 with EEG. Aim 2 will assess task 1 and 2 with MEG and concurrent EEG, task 3 with fMRI, and the 4th task will only be assessed as a behavioral task (no imaging).

Mood and Emotion Manipulations: Mood and emotion manipulation procedures will only be used in Aim 1 (EEG in Logan Hall) and not in Aim 2 (EEG, MEG, and MRI at the MRN). Mood manipulation will occur during EEG assessment, immediately prior to task performance.

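### Aim 1 asks whether mood and +RPE act independently or interactively on the RewP; the protocol promises modelling of this, but the only analysis described is a t-test with no +RPE variable

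*SAP*

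**What the plan says.** Protocol section 2 (Objectives) gives Aim 1 a directional prediction, that "a sadness manipulation in healthy controls should diminish the RewP", and a broader question. On the question it says: "Statistical modeling will quantify the independent vs. interactive influences of affective and +RPE processes on both the RewP and reward learning". It adds that "Computational modeling will identify the parameters best associated with the influence of affect on learning".

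Protocol section 3 (Background) says what each answer would mean. On one side, "The statistical interaction of depressed mood and poorer +RPE encoding would identify the RewP as a mechanism of diminished valuation in anhedonia". On the other, "if these are independent influences on the RewP (i.e. main effects), then diminished valuation is likely to be encoded in the downstream targets".

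Protocol section 8 (Study Methods) explains the choice of the Probabilistic Stimulus Selection task partly by its "three separately valued training pairs facilitates a wide range of +RPE values and assessments of reward vs. punishment learning".

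Section 7 (Study Endpoints) is marked N/A. The statistical paragraph in section 11 (Data Management) lists general neuroimaging methods, the general linear model among them, without naming mood or +RPE.

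The SAP of 03/15/2023 opens its ERP analysis with "we first aimed to conceptually replicate and extend findings" and then describes one test: "An independent-samples t-test was conducted between mood manipulation groups (sad vs. neutral) to test whether sad mood could relatively reduce the RewP". The outcome is average amplitude at FCz from 200 to 350 ms. No second analysis follows.

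**The concern.** The described test and the stated question do not match. The t-test asks whether the average RewP differs between sad and neutral groups. Aim 1 asks how mood and +RPE combine to produce the RewP, which requires +RPE to appear in the analysis.

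The interpretation depends on the answer: an interaction is to be read as the RewP being a mechanism of diminished valuation, and main effects alone as pointing downstream. If the t-test is the only evidence, either reading could be attached to the same result. The reward-learning outcome named in the same Aim 1 sentence also has no described test.

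**Working it through.** **Is there a plan figure to reproduce?** No. Neither document states an effect size, standard deviation, power, alpha or sidedness for this comparison. Section 25 gives 150 Aim 1 controls, but not how they divide between Aims 1a and 1b or between sad and neutral groups.

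**Is the interaction analysis specified anywhere?** Aim 1 names the two factors and the two outcomes. The Background names the contrast. Section 11 names a broad class of model. No place gives a model with a mood-by-+RPE term, the learning model that yields +RPE, the unit of analysis, or a rule for calling the effects independent or interactive.

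**What does the t-test estimate?** Write the amplitude on a reward trial as

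amplitude = b0 + b1·RPE + b2·sad + b3·sad·RPE

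Here b2 is the additive mood effect and b3 the change in +RPE slope under sadness. Averaging within each group:

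- sad: b0 + b1·E[RPE|sad] + b2 + b3·E[RPE|sad]
- neutral: b0 + b1·E[RPE|neutral]
- difference: b2 + b3·E[RPE|sad] + b1·(E[RPE|sad] − E[RPE|neutral])

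The t-test sees only this sum. A larger sample estimates the sum more precisely but does not separate its parts.

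**Numbers put in.** These values are assumed and only illustrate the formula: b1 = 6 µV per unit of RPE and mean +RPE 0.40 in both groups unless stated.

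| Situation | b2 | b3 | Shift in mean +RPE | Expected difference |
|---|---|---|---|---|
| Additive only | −1.2 | 0 | 0 | −1.2 |
| Slope halved only | 0 | −3 | 0 | −3 × 0.40 = −1.2 |
| Slope halved, offset by intercept | +1.2 | −3 | 0 | 1.2 − 1.2 = 0 |
| Additive, sad group's mean +RPE higher by 0.10 | −1.2 | 0 | +0.10 | −1.2 + 6 × 0.10 = −0.6 |

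The first two rows are the Background's two opposing answers, and they give the same expected difference. The third row is an interaction that the t-test cannot see. The fourth is an additive effect partly masked. For the sadness prediction, a mood-induced shift in mean +RPE is part of mood's total effect and not a bias; it matters only for the independent-versus-interactive question.

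**Does adding a mood-by-+RPE term settle the matter?** Not alone. Section 8 places the induction immediately before the tasks and tracks sadness at later time points. +RPE tends to shrink as values are learned. If sadness fades over the task, a purely additive effect is largest when +RPE is largest, which can look like an interaction.

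This was simulated under assumed inputs: reward rates 80/70/60%, 360 trials, choice sensitivity 3, 50 per group, trial noise 12 µV, slope SD 4, an additive effect averaging −1.2 µV and no true interaction. With sadness fading linearly to zero and no time term, a slope contrast rejected in 27%, 16%, 8% and 2% of 250 runs at learning rates 0.02, 0.05, 0.1 and 0.3. With constant mood it rejected in 4% to 6%. In a rerun of 200 runs per cell under assumed inputs, giving each participant a linear trial trend brought rejection to 3% to 8%, with the estimated b3 near zero. The risk therefore depends on how fast people learn and how fast sadness fades, and time terms address it when the fading is roughly linear.

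**The case against.** The strongest reply is that the protocol is not silent. Aim 1 commits to modelling independent versus interactive influences, and the Background says how to read the interaction. A reader might infer from the SAP that the interaction question was ignored or abandoned. The documents do not support that: the SAP confines itself to ERP data and presents the t-test as a first aim, so further steps may exist outside the supplied text. What stands is narrower. The modelling is promised but not specified, and a statement of intent without terms, a source for RPE or a decision rule cannot be checked against what is later reported.

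A reader might also infer that the t-test is wrong. It is not. It addresses the prediction that sadness diminishes the RewP and claims no more. Calling it suitable for that prediction does not vouch for a causal reading, since neither document describes the neutral condition, the allocation method or the sidedness.

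A third tempting inference is that the study is underpowered for the interaction. That cannot be shown. Trial counts, noise, spread of +RPE, between-person variation in slope and group sizes would all have to be assumed.

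Finally, the SAP is written in the past tense, so new text may come too late to count as pre-specification. That objection stands, and it limits what an edit can restore.

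**Conclusion.** The point holds in this form: Aim 1's independent-versus-interactive question has modelling promised in the protocol but no specified analysis in either document, and the one described test cannot answer it at any sample size. That conclusion rests on the algebra and on the absence of +RPE from the SAP, and on no assumed variance or effect size. The numerical table only illustrates it.

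The consequence is limited to interpretation of Aim 1. The sadness prediction keeps a suitable test. The point should be fixed, because the Background attaches different scientific conclusions to two answers that the described analysis cannot tell apart. How often an interaction would be missed or misattributed in this study cannot be put as a figure from the documents.

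**What to change.** Keep the t-test for the sadness prediction, and change the SAP as follows:

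- **Contrast.** Name a mood-by-+RPE contrast on reward trials as the Aim 1 test. One form is a trial-level mixed model with mood, RPE and mood:RPE, and a random intercept and RPE slope per participant. The other is a group comparison of per-participant RewP-on-RPE slopes. Power was nearly the same in one simulation with assumed inputs (53% and 52%), so the choice is secondary.
- **RPE.** State the learning model that yields RPE, and centre RPE at one value common to both groups so that the mood term is the difference at equal RPE.
- **Time.** Include trial number and mood-by-trial, or the repeated sadness ratings described in section 8 if their timing covers the task. In the slope-comparison form, fit a trial trend for each participant. A linear term need not fully remove fading that is faster than linear, so the form should be justified.
- **Reporting.** Give the interaction with its confidence interval, and do not read a non-significant interaction as independence.
- **Reward learning.** Name the measure and add a mood comparison for it.
- **Status.** Label the model post hoc unless earlier specification can be documented.

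The cost is SAP text and modest analysis, using EEG, choices and outcomes from a task already in the protocol. The downsides are that results will depend on the learning model, that the time terms cost some precision, and that power cannot be fixed from the documents.
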